2. LIST OF ABBREVIATIONS

AE	Adverse Event
CI	Confidence Interval
EudraCT	European Clinical Trials Database
FAS	Full Analysis Set
IEC	Independent Ethics Committee
IRB	Institutional Review Board
i.v.	Intravenous
MedDRA	Medical Dictionary for Drug Regulatory Activities
OAD	Oral Antidiabetic Drugs
OPU	Operative Unit
p.o.	per os (oral)
q.d.	quaque die (once a day)
SAE	Serious Adverse Event
s.c.	Subcutaneous
T2DM	Type 2 Diabetes Mellitus
TCM	Trial Clinical Monitor
t.i.d.	ter in die (3 times a day)
TMM	Team Member Medicine

4. ABSTRACT

Name of company: Boehringer Ingelheim			
Name of finished medicinal product: If applicable, list centrally-authorised medicinal product(s) subject to the study.		Trazenta	
Name of active ingredient: List pharmacotherapeutic group(s){ACT codes} and active substance(s) subject to the study		A10N,A10H,A10J,A10K,A10L A10M	
Protocol date: 09 February 2017	Study number: 1218.178	Version/Revision: 1.0	Version/Revision date:
Title of study:	Clinical characteristics and practice patterns of type 2 diabetes mellitus (T2DM) patients treated with oral antidiabetic drugs (OADs) in Japan: analysis of medical and health care database of the Medical Data Vision (MDV)		
Rationale and background:	
Renal impairment (RI) is a common complication in patients with type 2 diabetes. In Japanese patients with T2DM, about 40% of patients have microalbuminuria or macroalbuminuria, and other report shows that 55% of Japanese patients with T2DM suffer from mild to moderate renal dysfunction.
 
Many of OADs are contraindicated in severe RI patients or should be carefully administered in patients with declined renal function. For biguanide, a risk of lactic acidosis increases in RI and biguanide is contraindicated in moderate or severe RI. SU and Glinides require caution of a risk of hypoglycemia including prolonged hypoglycemia in patients with RI. Pioglitazone is used with no contraindication in patients with RI in USA, meanwhile in Japan it is contraindicated in severe RI patients and it requires careful administration to mild to moderate RI patients. Alpha-glucosidase inhibitors (α-GIs) also require careful administration in RI patients although the levels of severity of RI with caution are different from each drug in some measure.
 
The prescriptions of DPP-4 inhibitors are rapidly increasing in T2DM patients after its introduction to the Japanese clinical practice in 2009. The reason of this trend might result from well-balanced drug characteristics with its safety profile, especially low frequency of hypoglycaemia and its acceptable efficacy on blood glucose lowering. Therefore many of physicians consider DPP-4 inhibitor is widely chosen as a monotherapy and one of combination therapy.
 
As for DPP-4 inhibitors administered on a daily basis, there are seven single ingredient drugs in this class and their dose-reduction manners are various in RI patients. Linagliptin and teneligliptin are not required dose reduction. On the other hand, other five drugs are recommended dose
		

Name of company: Boehringer Ingelheim			
Name of finished medicinal product: If applicable, list centrally-authorized medicinal product(s) subject to the study.		Trazenta	
Name of active ingredient: List pharmacotherapeutic group(s){ACT codes} and active substance(s) subject to the study		A10N,A10H,A10J,A10K,A10L A10M	
Protocol date: 09 February 2017	Study number: 1218.178	Version/Revision: 1.0	Version/Revision date:
		
reduction or careful administration as excretion might be delayed and blood levels also might rise in patients with RI due to the mechanism of renal excretion. Furthermore sitagliptin and alogliptin have four and three of drug formulations of different contained amount respectively in Japan. Japanese physicians are required proper use of complicated regimen in accordance with each patient's renal function.
 
Thus, appropriate use of OADs including dose-reduction is important for patient's safety in T2DM patients with RI. However, there are insufficient data on dose adjustment in accordance with the prescription pattern and the risk of RI of OADs, in particular DPP-4 inhibitors, in clinical practice in Japan. Therefore, we will investigate OADs usage conditions in T2DM patients by using Medical Data Vision clinical database in clinical practice in Japan.
	
Research question and objectives:	
Research question: To understand the prescription pattern in T2DM patients of each compound and each class for all OADs, available throughout study period.
 
Study objectives:
 
 To analyze the demographic and clinical characteristics of T2DM patients who have been treated with OADs 
■ [REDACTED]
 
■ [REDACTED]
		
Study design:	Descriptive cohort study		
Population:	
Medical Data Vision (MDV) clinical database is used.
 
Inclusion criteria:
 
 Patients with T2DM 		

Name of company: Boehringer Ingelheim			
Name of finished medicinal product: If applicable, list centrally-authorized medicinal product(s) subject to the study.		Trazenta	
Name of active ingredient: List pharmacotherapeutic group(s){ACT codes} and active substance(s) subject to the study		A10N,A10H,A10J,A10K,A10L A10M	
Protocol date: 09 February 2017	Study number: 1218.178	Version/Revision: 1.0	Version/Revision date:
	
 · Patients must have their first prescription for any study drugs between 01/01/2014 and 30/09/2016. The index date will be set as the first prescription of each drug during the study period. · Patients must have at least 6 month enrolment verified by the presence of any record except for the study drug prescriptions within the database (look back period) prior to the index date for each drug. 
Exclusion criteria:
 
 · Patients who were under 40 y.o. at the time of diagnosis of diabetes. · Patients with record of type 1 diabetes mellitus. · Patients who prescribed the study drugs during 6 month prior to index date for each drug. · Patients whose mean visit interval are more than 92 days 		
Variables:	Number of patients, age at index date, sex, prior and concomitant use of glucose-lowering medications and insulin, comorbidities, serum creatinine. eGFR will be calculated using serum creatinine, age, and sex.		
Data sources:	
Medical Data Vision (MDV) clinical database. The database is health insurance claim database. As of end of July 2015, facilities: 200, patients: 10.95 million, which is covering approximately 12% of acute hospitals in Japan. Lab results are also available but number of hospitals providing with lab test results are limited.
 
Study period is from 01/01/2014 to 30/09/2016 in MDV database at the time of study protocol approval.
 
The MDV database is broadly representative of the Japanese population with similar distribution comparing with Japanese population; therefore we believe our study sample will provide reasonable description of the characteristics of patients treated with diagnosis of type 2 diabetes mellitus in the general Japanese population. There is research experience using the data, 19 publications, 5 conference presentations (as of August 2015).
		
Study size:	
All available data from 01/01/2014 to 30/09/2016 will be included to ensure the maximum number of patient.
 
All patients with a prescription of OADs and DPP-4 inhibitors from
		

Name of company: Boehringer Ingelheim			
Name of finished medicinal product: If applicable, list centrally-authorized medicinal product(s) subject to the study.		Trazenta	
Name of active ingredient: List pharmacotherapeutic group(s){ACT codes} and active substance(s) subject to the study		A10N,A10H,A10J,A10K,A10L A10M	
Protocol date: 09 February 2017	Study number: 1218.178	Version/Revision: 1.0	Version/Revision date:
		
01/01/2014 to 31/08/2015 and a diagnosis of T2DM is estimated that approximately 9,890 and 7,579 patients respectively have been prescribed a study drug in the MDV database to be included in the study.
 
The power calculation has not been conducted as there will not be any hypothesis testing in the analysis. Data of MDV is from all DPC hospitals. Data is collected directly from hospitals, so it holds every data of all insurances.
 
Limitaion: Number of hospitals providing with lab test results are limited.
	
Data analysis:	
 • For the 1st objective, descriptive statistics of each compound and each class of OAD will be presented for the baseline demographic and clinical characteristics: 
 • Number of patients • Age (mean ± SE, mean ± SD) • Concomitant medications (drug prescribed at index day) : 
 • Use of biguanide (Yes/No) • Use of sulfonylurea (Yes/No) • Use of thiazolidinediones (Yes/No) • Use of glinide (Yes/No) • Use of α-GI (Yes/No) • Use of GLP-1RA (Yes/No) • Use of SGLT2 inhibitors (Yes/No) • Use of insulin (Yes/No) • Premedications (drug prescribed before index day): 
 • Use of biguanide (Yes/No) • Use of sulfonylurea (Yes/No) • Use of thiazolidinediones (Yes/No) • Use of glinide (Yes/No) • Use of α-GI (Yes/No) • Use of GLP-1RA (Yes/No) • Use of SGLT2 inhibitors (Yes/No) 		

Proprietary confidential information © 2017 Boehringer Ingelheim International GmbH or one or more of its affiliated companies

Name of company: Boehringer Ingelheim			
Name of finished medicinal product: If applicable, list centrally-authorized medicinal product(s) subject to the study.		Trazenta	
Name of active ingredient: List pharmacotherapeutic group(s){ACT codes} and active substance(s) subject to the study		A10N,A10H,A10J,A10K,A10L A10M	
Protocol date: 09 February 2017	Study number: 1218.178	Version/Revision: 1.0	Version/Revision date:
	
 • Use of insulin (Yes/No) • Comorbidities: 
 • Hypertension: Percentage of patients with a diagnosis of hypertension • Ischemic heart disease (IHD): Percentage of patients with a diagnosis of IHD • Myocardial Infarction (MI): Percentage of patients with a diagnosis of MI • Heart Failure (HF): Percentage of patients with a diagnosis of HF • Stroke: Percentage of patients with a diagnosis of stroke • Renal impairment: Percentage of patients with a diagnosis of renal impairment • Amputation: Percentage of patients with a diagnosis of amputation 		

Name of company: Boehringer Ingelheim			
Name of finished medicinal product: If applicable, list centrally-authorized medicinal product(s) subject to the study.		Trazenta	
Name of active ingredient: List pharmacotherapeutic group(s){ACT codes} and active substance(s) subject to the study		A10N,A10H,A10J,A10K,A10L A10M	
Protocol date: 09 February 2017	Study number: 1218.178	Version/Revision: 1.0	Version/Revision date:
Milestones:	Submission to IRB (Keio University)		10 th February 2017
	IRB (Keio University) meeting		17 th February 2017
	Registration to clinicaltrials.gov and ENCePP		28 th February 2017
	Start of data analysis		1 st March 2017
	Start of manuscript preparation		1 st March 2017
	End of data analysis		10 th March 2017
	Draft study report		31 st March 2017
	Final report of study results		20 th April 2017
	Submission of manuscript to Journal		26 th June 2017

5. AMENDMENTS AND UPDATES

Number	Date	Section of study protocol	Amendment or update	Reason
	None			

6. MILESTONES

Milestone	Planned Date
Submission to IRB (Keio University)	10 th February 2017
IRB (Keio University) meeting	17 th February 2017
Registration to clinicaltrials.gov and ENCePP	28 th February 2017
Start of data analysis	1 st March 2017
Start of manuscript preparation	1 st March 2017
End of data analysis	10 th March 2017
Draft study report	31 st March 2017
Final report of study results	20 th April 2017
Submission of manuscript to Journal	26 th June 2017

7. RATIONALE AND BACKGROUND

Renal impairment (RI) is a common complication in patients with T2DM. In Japanese patients with T2DM, about 40% of patients have microalbuminuria or macroalbuminuria [1], and other report shows that 55% of Japanese patients with T2DM suffer from mild to moderate renal dysfunction [2].

Many of OADs are contraindicated in severe RI patients or should be carefully administered in patients with declined renal function. For biguanide, a risk of lactic acidosis increases in RI and biguanide is contraindicated in moderate or severe RI. Pioglitazone is used with no contraindication in patients with RI in USA, meanwhile in Japan it is contraindicated in severe RI patients and it requires careful administration to mild to moderate RI patients. Glinides and α -GIs also require careful administration in RI patients although the levels of severity of RI with caution are different from each drug in some measure.

The prescriptions of DPP-4 inhibitors are rapidly increasing in T2DM patients after its introduction to the Japanese clinical practice [3]. The reason of this trend might result from well-balanced drug characteristics with its safety profile, especially low frequency of hypoglycaemia and its acceptable efficacy on blood glucose lowering. Therefore many of physicians consider DPP-4 inhibitor is widely chosen as a monotherapy and one of combination therapy.

As for DPP-4 inhibitors administered on a daily basis, there are seven single ingredient drugs in this class and their dose-reduction manners are various in RI patients. Linagliptin and teneligliptin are not required dose reduction. On the other hand, other five drugs are recommended dose reduction or careful administration. Furthermore sitagliptin and alogliptin have four and three of drug formulations of different contained amount respectively in Japan. Japanese physicians are required proper use of complicated regimen in accordance with each patient's renal function.

Currently, there is no publication of actual situation on the prescription patterns of OADs and dose-reduction especially in DPP-4 inhibitors and other OADs needed to dose-reduction. However from viewpoint of appropriate use, relevant dose-reduction can contribute patients benefit. This study aims to assess the actual condition of dose selection of OADs among RI patients in Japan by using MDV database.

MDV provides commercial claims database for inpatient and outpatient consisting medical records from more than 12.94 million patients from 230 large acute care DPC hospitals as of Feb 2016. According to the data released by the company in Sept 2016 [1], in one year period between July 2015 and June 2016, cumulative number of patients in the claims database was 7,546,862 patients. 82% of patients (6,152,732) were associated with outpatient claims only, while 15% of patients (1,131,869) had claims from both in and out-patient care. Only 3% of patients (262,261) had exclusively in-patient claims. Laboratory data is available for approximately 10% of patients contained in the database. The DPC is a case-mix system, similar to Medicare in the US. It comprises of 18 Major Diagnosis Categories, 520 diagnostic groups and 2,658 case-mix groups. In the DPC algorithm, the diagnosis, procedure and comorbidities/complications are the 3 key variables for classification. The diagnosis and comorbidities/complications are coded using the ICD10 scheme, while the procedures are coded using the Japanese Procedure Codes. Not only administrative claims data but also

detailed patient data are collected for all the inpatients discharged from the participating hospitals.

[figure not shown]
8. RESEARCH QUESTION AND OBJECTIVES

Research question:

To understand the prescription pattern in T2DM patients of each compound and each class for all OADs, available throughout study period i.e. DPP-4 inhibitors, sulfonylureas, biguanides, thiazolidinediones, α -GIs, glinides.

Study objectives:

1. To analyze the demographic and clinical characteristics of T2DM patients who have been treated with OADs

9. RESEARCH METHODS

9.1 STUDY DESIGN

Study design:

- Descriptive cohort study

Comparison group

- OAD group, DPP-4 inhibitors group, SU group, BG group, TZD group, α -GI group, and Glinide group.

Strength of the study design

- Up-to-date information can be obtained and nationwide actual treatment status can be illustrated with using large-scale real-world database.

Analysis

- First analysis: type and dosage of drug prescribed for T2DM patients.
- [REDACTED]
- Main measures: number of patients, baseline characteristics at index month (age, sex), prior and concomitant use of glucose-lowering medications and insulin (type, dose), comorbidities (types and their percentages of patients), stage of RI defined by eGFR or serum creatinine value, glucose-lowering medications and their dosages (based on daily dose) for patients with RI, [REDACTED]
- [REDACTED]

Potential limitation

- The data held in MDV database is collected from DPC hospitals, not GP data. However they are including outpatient data because many of Japanese patients prefer to visit a hospital even though chronic disease.
- The rate of laboratory test data held in MDV database is limited. About 350,000 patients out of 2,600,000 patients (13.5%, April 2008 ~ April 2016) have laboratory data.
- The MDV database does not hold the time diagnosis of T2DM if it is out of study period. Therefore the onset date of diabetes or the first record of T2DM cannot obtain for all patients.
- The information on medication is based on prescribed record, not include adherence result. It means that exact dosage may not reveal actual dispensed prescription and dosage perfectly.
- Laboratory test date is not exactly matched with the index day of the first prescription of OAD. The sample size will have some impacts (reduction) to assure simultaneous timing of data. The latest lab result 30 days before the index date will be considered the status at the time of prescription
- All information of each patient is from consent given DPC hospitals. If patients have visits to other medical institutions, these data are not included in the MDV data.

- MDV database is composed of data from patients who hospitalized in DPC hospital so that more severe patient will be included in the database.

9.2 SETTING

Medical Data Vision (MDV) clinical database is used.

Inclusion criteria

[figure not shown]
- Patients with T2DM (ICD code: E11 or E14).
- Patients must have their first prescription (defined as index date*) for any study drugs between 01/01/2014 and 30/09/2016.
- Patients must have at least 6 months enrolment verified by the presence of any record except for the study drug prescriptions within the database (look back period) prior to the index date for each drug.

Exclusion criteria

- Patients who were under 40 y.o. at the time of diagnosis of diabetes.
- Patients with record of type 1 diabetes mellitus (ICD code: E10).
- Patients who prescribed the study drugs during 6 month prior to index date for each drug.
- Patients whose mean visit interval are more than 92 days

*Index date is defined as follows:

- In case of comparing drugs within class, index date is defined as the date of first prescription for any study drugs as general name. Change of dosage is not counted as the index.
- In case of comparing drugs between class, index date is defined as the date of first prescription for study drug of class. Change of dosage is not counted as the index.

* The hospitalization period is not included in the mean visit interval.

Figure 1 Definition of Index data(date of first prescription for any study drugs)

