9.5 STUDY SIZE

All available data from 01/01/2014 to 30/09/2016 will be included to ensure the maximum number of patient.

All patients with a prescription of OADs and DPP-4 inhibitors from 01/01/2014 to 31/08/2015 and a diagnosis of T2DM is estimated that approximately 9,890 and 7,579 patients respectively have been prescribed a study drug in the MDV database to be included in the study.

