9.9 LIMITATIONS OF THE RESEARCH METHODS

- The data held in MDV database is collected from DPC hospitals, not GP data. However they are including outpatient data because many of Japanese patients prefer to visit a hospital even though chronic disease.
- The rate of laboratory test data held in MDV database is limited. About 350,000 patients out of 2,600,000 patients (13.5%, April 2008 ~ April 2016) have laboratory data.
- The MDV database does not hold the time diagnosis of T2DM if it is out of study period. Therefore the onset date of diabetes or the first record of T2DM cannot obtain for all patients.
- The information on medication is based on prescribed record, not include adherence result. It means that exact dosage may not reveal actual dispensed prescription and dosage perfectly.
- Laboratory test date is not exactly matched with the index day of the first prescription of OAD. The sample size will have some impacts (reduction) to assure simultaneous timing of data. The latest lab result 30 days before the index date will be considered the status at the time of prescription
- All information of each patient is from consent given DPC hospitals. If patients have visits to other medical institutions, these data are not included in the MDV data.
- MDV database is composed of data from patients who hospitalized in DPC hospital so that more severe patient will be included in the database.

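### Section 9.2 counts a patient as T2DM when the record holds E14 plus E12 or E13 and no E11, and E14-only patients are pooled with E11 patients without a visible split

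*Combined protocol and SAP*

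**What the plan says.** The inclusion criterion in section 9.2 is "Patients with T2DM (ICD code: E11 or E14"; an E14 record does not need a confirming E11. Among diabetes-type codes, the only exclusion is "Patients with record of type 1 diabetes mellitus (ICD code: E10". Another exclusion bears on type indirectly, through age: "Patients who were under 40 y.o. at the time of diagnosis of diabetes". The remaining criteria concern prescription timing, look-back and visit interval.

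The abstract gives the same criteria without codes. Codes E12 and E13 do not appear anywhere in the visible text. On the coding system, section 7 states: "The diagnosis and comorbidities/complications are coded using the ICD10 scheme".

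The visible objective in section 8 is "To analyze the demographic and clinical characteristics of T2DM patients who have been treated with OADs". Section 9.7.1 lists the characteristics to be tabulated for each compound and each class. The visible part of that list has no breakdown by diabetes code and no analysis restricted to E11. The limitations in 9.1 and 9.9 and the bias section 9.12 do not mention misclassification of diabetes type.

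**The concern.** The plan already accepts that a code for a competing diabetes type should remove a patient, since it does this for E10. It gives no reason for treating E12 and E13 differently. The inclusion side is also permissive, because E14 leaves the type open. Together, the two rules let in a patient whose record names a type other than type 2 and never names type 2.

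What is at stake is the label on the tables. The visible objective is a description of T2DM patients, so the case definition decides what every reported percentage refers to. A reader of the abstract sees only that patients have T2DM and cannot tell that unspecified diabetes qualifies. A reader of the results could not tell how much of each drug group rests on E14 alone.

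**Working it through.** There is no stated figure to reproduce, and no sample-size formula applies: the abstract says "The power calculation has not been conducted as there will not be any hypothesis testing in the analysis". The check is to apply the criteria of section 9.2 to each combination of codes.

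Inputs:
- Inclusion on E11 or E14, and exclusion on E10: section 9.2.
- ICD-10 as the coding scheme: section 7.
- Meaning of the codes: the plan does not spell it out. The standard ICD-10 labels are assumed, with E11 type 2, E14 unspecified, and E12 and E13 other specified types.
- All other criteria are taken as met, and no E10 is on record unless shown.

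| Codes on record | Result under 9.2 as written | Does the record support the T2DM label? |
|---|---|---|
| E11, with or without E14 | Included | Yes |
| E14 only | Included | Type not stated |
| E11 or E14, plus E10 | Excluded | Not applicable |
| E14 plus E12 or E13, no E11 | Included | No; the only named type is another one |
| E11 plus E12 or E13 | Included | Mixed; type 2 is also named |
| E12 or E13 only | Not included | Not applicable |

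The fourth row is the gap in the exclusion rule. The second row is the group that is pooled without being counted.

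Next, do other parts of the plan close the fourth row?
- The age rule removes anyone diagnosed with diabetes before 40, whatever the type. It does not identify type in a patient diagnosed later. Section 9.9 also concedes that it cannot be applied to everyone: "Therefore the onset date of diabetes or the first record of T2DM cannot obtain for all patients".
- Entry requires a prescription from the list in section 9.3.1. Those are glucose-lowering drugs, and nothing in the plan makes a prescription evidence of type.
- Quality control in section 9.8 covers program code, calculation, methodology and consistency of results. It adds no rule on diabetes codes.

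None of these removes the patient in the fourth row.

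Size: the affected share is (patients with E14 and with E12 or E13, and no E11) / (all included patients). The documents give neither the numerator nor any code frequency, so the share cannot be calculated. The only usable figure is the expected study size in section 9.5, "approximately 9,890 and 7,579 patients respectively have been prescribed a study drug in the MDV database to be included in the study", for OADs and DPP-4 inhibitors respectively. It converts shares to heads: 1% would be 0.01 × 9,890 = 98.9, about 99 OAD patients, and 0.01 × 7,579 = 75.8, about 76 DPP-4 inhibitor patients. The 1% is a unit of scale and not an estimate. Section 9.5 counts prescriptions only to 31/08/2015, while the study period runs to 30/09/2016.

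**The case against.** The strongest defence is that this is a disclosed operational definition in a descriptive study. Accepting E14 trades specificity for coverage, the codes are printed in section 9.2, and no hypothesis is tested. The age rule and the drug requirement filter out some patients with other types. Parts of the plan are also blacked out, including analysis items in 9.1 and a section after 9.7.1, so an E11-only analysis may exist there.

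Much of this stands. Accepting E14 is a legitimate choice, and the point does not ask for it to be dropped. The filters are partial but not irrelevant. Because of the blacked-out text, one can say only that no split or E11-only table is visible. The code lists in 9.2 are complete sentences, however, and show no sign of a removed E12/E13 exclusion, so the gap in the exclusion rule stands.

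Three stronger readings are tempting, and the documents do not support them.
- A reader might infer that a material percentage of the cohort is misclassified, for example by multiplying a guessed E14-only share by a guessed share of those who are not type 2. Every input would be assumed. The product would also describe E14-only patients, who carry no E12 or E13 code and whom an exclusion on those codes would not remove.
- A reader might infer that the misclassification differs between compounds or classes and so distorts drug comparisons. Nothing in the documents shows this.
- A reader might infer that every patient with an E12 or E13 code is wrongly labelled. With E11 also on record, the record names type 2 as well, and calling that patient T2DM is not shown to be wrong. Removing such patients would take E11-coded people out of the target population.

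**Conclusion.** The point holds in a narrow form. Under section 9.2 as written, a patient with E14 plus E12 or E13 and no E11 is described as T2DM although the only named type is another one. Patients with E14 alone are merged with E11 patients without a visible count.

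This rests on the standard meaning of the ICD-10 categories and on the visible text being the full code list. The size is unknown and cannot be derived from the documents; it may be negligible. The consequence is confined to how the described population is labelled. It is a cheap improvement, not a flaw that threatens the study.

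**What to change.** In section 9.2, add an exclusion for patients with an E12 or E13 record and no E11 record, searched over the same part of the record as E10. State the code definition and this exclusion in the abstract as well.

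In section 9.7.1, report by class and by compound the number of patients with E11, with E14 only, and with co-recorded E12 or E13. Split the last group by whether E11 is present (kept) or absent (removed). Repeat the main characteristics table in E11-coded patients. If the two tables agree, the T2DM label is strengthened; if they differ, readers can see by how much.

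The cost is a short condition in the selection program and one extra table from data already held. The downside is the loss of a few true T2DM patients coded E14 with a stray E12 or E13, a loss of the kind the plan already accepts for E10. Patients with an E11 record are not affected by the new exclusion.

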11. MANAGEMENT AND REPORTING OF ADVERSE EVENTS/ADVERSE REACTIONS

The outcomes of the study are the baseline characteristics (pre-treatment) and medication prescriptions. We will not be looking at outcomes during the treatment period; therefore safety reporting is not applicable for this study.

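### The only stated proof of 6 months' enrolment is a non-study-drug record in the look-back, so as worded a recent arrival already treated elsewhere can pass the washout

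*Combined protocol and SAP*

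**What the plan says.** Section 9.2 (repeated in the population row of the Abstract) sets three conditions that bear on this point.

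- **Index date:** "Patients must have their first prescription (defined as index date*) for any study drugs between 01/01/2014 and 30/09/2016".
- **Enrolment:** at least 6 months before the index date for each drug, "verified by the presence of any record except for the study drug prescriptions within the database (look back period").
- **Washout**, as an exclusion: "Patients who prescribed the study drugs during 6 month prior to index date for each drug".

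A further exclusion removes "Patients whose mean visit interval are more than 92 days". The period over which that mean is taken is not stated.

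On what the database can see, Section 9.9 says "The data held in MDV database is collected from DPC hospitals, not GP data" and "If patients have visits to other medical institutions, these data are not included in the MDV data". Section 9.1 repeats both statements, and Section 9.12 repeats the second.

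Section 9.7.1 tabulates premedication as Yes or No by drug class. Section 11 says "The outcomes of the study are the baseline characteristics (pre-treatment) and medication prescriptions".

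**The concern.** The criterion names a length of history but gives a check that does not measure length. Any qualifying record in the look-back shows that the patient was known to the hospital at some point in those 6 months. It does not show that the patient was observed throughout them.

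The washout relies on that observation. A prescription issued elsewhere before the patient arrived leaves no trace, so an unobserved stretch of the washout is counted as drug-free.

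Two outputs are at stake. The premedication table would understate earlier treatment, because drugs prescribed elsewhere appear as No. The pre-treatment description of baseline would also be wrong for these patients. The error lies in the descriptive tables themselves, and a larger sample would not reduce it.

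**Working it through.** No formula in the plan applies: the study is descriptive, and the Abstract says that no power calculation was done. The check is to apply the Section 9.2 rules to constructed patients. Day 0 is the index date, and 6 months is taken as about 182 days.

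**Case A: recent arrival, drug already prescribed elsewhere.** One non-drug record on day -14, first prescription in the database on day 0, visits on days 28, 56 and 84.

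- Enrolment as worded: there is a non-study-drug record in the look-back, so it passes.
- Washout: there is no study drug in the database in the prior 6 months, so it passes.
- Visit interval: (14 + 28 + 28 + 28) / 4 = 98 / 4 = 24.5 days, below 92, so it passes. This filter measures how often a patient attends, not how long the history is.
- Unobserved washout: 182 - 14 = 168 days, and 168 / 182 = 92%.

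The patient enters as a first-prescription patient.

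**Case B: recent arrival, drug continued at the very first visit.** There is no earlier record, so the present rule already excludes this patient.

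**Case C: patient attending the hospital for more than 6 months for another condition, with the drug prescribed elsewhere and later taken over by the hospital.** There is a long history and no study drug in the database.

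**Case D: recently registered patient with a genuine first prescription.** Same record pattern as Case A.

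| Case | Rule as worded | With a record required 6 months or more before index |
|---|---|---|
| A | included | excluded |
| B | excluded | excluded |
| C | included | included |
| D | included | excluded |

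A date filter therefore closes the route in Case A, leaves the one in Case C open, and costs some patients like Case D. Cases A and D look the same in the data. The number of patients the filter removes is therefore an upper limit on the number in Case A.

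**Scale.** Section 9.5 estimates 9,890 patients with an oral antidiabetic prescription from 01/01/2014 to 31/08/2015, which is only part of the study period. Each 1% of that count is 0.01 x 9,890 = about 99 patients. No document gives the share with a short history, or the share of those already treated elsewhere.

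**The case against.** The strongest reply is that the sentence opens by requiring at least 6 months' enrolment. The words about any record may only say which type of record counts. On that reading a patient first seen a week before index fails, and the proposed filter is already the rule. Figure 1, which defines the index date, is not shown in the text available and might settle this. A reader might infer that the plan definitely takes a single late record as proof. The documents do not establish that. What stands is that the visible text states no other check, so a programmer could follow it and accept any record.

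The second reply is that outside care is already disclosed as missing. It is, three times, but only in general terms. None of those statements links it to the index date, the washout or the premedication table.

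The third reply concerns harm, and part of it stands.

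- A reader might infer that the dose outcome is invalid because a continuing dose is not a starting dose. Section 9.3.2.2 asks for drug and daily dose in the index month by renal function, and Section 7 asks about dose selection in patients with renal impairment. Neither restricts this to starting doses, so a continued dose is still a valid observation.
- Nor is all premedication lost. Prescriptions recorded at the hospital before index are still captured, and only those from outside are missing. For the index drug itself, the exclusion criterion imposes absence in the prior 6 months on everyone.

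Finally, the filter does not cure the underlying gap, as Case C shows, and it removes some genuine first prescriptions.

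**Conclusion.** The point holds as a weakness in how the enrolment criterion is verified. As worded, Section 9.2 can admit recently arrived patients with most of the washout unobserved, and the 92-day filter does not prevent it. Some would already be on treatment from another institution, so their outside premedication would be recorded as No and the pre-treatment description in Section 11 would not fit them.

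This rests on two things: that the criterion is programmed as its visible wording allows, and that some patients were prescribed the drug elsewhere before arrival. The documents confirm that such prescriptions would not be seen, but not how common they are. The number affected cannot be derived, and any percentage of the cohort would be an assumption with no anchor in the plan.

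No hypothesis test or sample-size figure is affected. The dose-by-renal-function outcome is not undermined. The change is worth making because it improves the premedication table and the baseline description at little cost.

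**What to change.** 1. In Section 9.2 and the Abstract, require at least one record dated 6 months or more before the index date, in addition to the non-study-drug record in the look-back. If this was already intended, say so in the criterion.
2. Report how many patients the requirement removes, by compound and by class. This bounds the recent-arrival problem, which the documents cannot size.
3. Describe the index as the first recorded prescription in the database, and qualify the pre-treatment wording in Section 11 to match.
4. In Sections 9.9 and 9.12, state as a limitation of the washout that long-standing hospital patients whose drug was prescribed elsewhere still pass, and that their outside premedication appears as No.

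The first two items need one date filter and a count on data already held; the other two are wording. The downside is a somewhat smaller cohort, including the loss of some genuine first prescriptions in recently registered patients. The study has no power target, so no planned precision is breached.
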